Repeat for Visits 4, 5,	6 and EOS.				
Test Product: Podofilo Reference: Condylox® Placebo: vehicle that n	x Topical Gel 0.5% Gel 0.5% natches the test product				
Source: <dataset></dataset>		Listing: 16.2		Snapshot	Data DD-MMM-YYYY
Program Name: <pgm< td="">name>	Date: YYYY-MN	1-DD Time: HH:MM:SS	Programmer	: <programmer initials=""></programmer>	</pgm<>	name>	Date: YYYY-MN	1-DD Time: HH:MM:SS	Programmer	: <programmer initials=""></programmer>

Protocol: 16-POD-001 Version 2.0, 15-Jan-2018

STATISTICAL ANALYSIS PLAN

Confidential

		Sum	iary of vitar orgins, o	urery ropulation		
Visit	Vital Sign	Statistic	Test Product	Reference	Placebo	All Subjects
Baseline (Day 0)	Temperature	n	XX	XX	XX	XX
	(°C)	Mean (SD)	xx.x (xx.xxx)	xx.x (xx.xxx)	xx.x (xx.xxx)	xx.x (xx.xxx)
		CV	XX.X	XX.X	XX.X	XX.X
		Median	XX.X	XX.X	XX.X	XX.X
		Min, Max	XX.X, XX.X	XX.X, XX.X	XX.X, XX.X	XX.X, XX.X
	Heart Rate	n	XX	XX	XX	XX
	(beats per	Mean (SD)	xx.x (xx.xxx)	xx.x (xx.xxx)	xx.x (xx.xxx)	xx.x (xx.xxx)
	minute)	CV	XX.X	XX.X	XX.X	XX.X
		Median	XX.X	XX.X	XX.X	XX.X
		Min, Max	XX.X, XX.X	XX.X, XX.X	XX.X, XX.X	XX.X, XX.X
	Systolic BP	n	XX	XX	XX	XX
	(mmHg)	Mean (SD)	xx.x (xx.xxx)	xx.x (xx.xxx)	xx.x (xx.xxx)	xx.x (xx.xxx)
		CV	XX.X	XX.X	XX.X	XX.X
		Median	XX.X	XX.X	XX.X	XX.X
		Min, Max	XX.X, XX.X	XX.X, XX.X	XX.X, XX.X	XX.X, XX.X
	Diastolic BP	n	XX	XX	XX	XX
	(mmHg)	Mean (SD)	xx.x (xx.xxx)	xx.x (xx.xxx)	xx.x (xx.xxx)	xx.x (xx.xxx)
		CV	XX.X	XX.X	XX.X	XX.X
		Median	XX.X	XX.X	XX.X	XX.X
		Min, Max	XX.X, XX.X	XX.X, XX.X	XX.X, XX.X	XX.X, XX.X
Repeat for visits 3, 4	4, 5 and 6.					
Test Product: Podof Reference: Condylo Placebo: vehicle tha	ilox Topical Gel (x® Gel 0.5% t matches the test).5% product				

Table 14.3.1.1Summary of Vital Signs, Safety Population

Source: <Dataset>

Listing: 16.3.1

Program Name: <Pgm name>

Date: YYYY-MM-DD Time: HH:MM:SS

Snapshot Data DD-MMM-YYYY

Programmer: < Programmer Initials>

Protocol: 16-POD-001 Version 2.0, 15-Jan-2018

Confidential

		vitai	Signs Changes from Ba	senne, Salety Populat	1011	
Visit	Vital Sign	Statistic	Test Product	Reference	Placebo	All Subjects
Visit 3 (Day 7)	Temperature (°C)	n Mean (SD)	xx xx.x (xx.xxx)	xx xx.x (xx.xxx)	xx xx.x (xx.xxx)	xx xx.x (xx.xxx)
		CV	XX.X	XX.X	XX.X	XX.X
		Median	XX.X	XX.X	XX.X	XX.X
		Min, Max	XX.X, XX.X	XX.X, XX.X	XX.X, XX.X	XX.X, XX.X
	Heart Rate	n	XX	XX	XX	XX
	(beats per	Mean (SD)	xx.x (xx.xxx)	xx.x (xx.xxx)	xx.x (xx.xxx)	xx.x (xx.xxx)
	minute)	CV	XX.X	XX.X	XX.X	XX.X
		Median	XX.X	XX.X	XX.X	XX.X
		Min, Max	XX.X, XX.X	XX.X, XX.X	XX.X, XX.X	XX.X, XX.X
	Systolic BP	n	XX	XX	XX	XX
	(mmHg)	Mean (SD)	xx.x (xx.xxx)	xx.x (xx.xxx)	xx.x (xx.xxx)	xx.x (xx.xxx)
		CV	XX.X	XX.X	XX.X	XX.X
		Median	XX.X	XX.X	XX.X	XX.X
		Min, Max	XX.X, XX.X	XX.X, XX.X	XX.X, XX.X	XX.X, XX.X
	Diastolic BP	n	XX	XX	XX	XX
	(mmHg)	Mean (SD)	xx.x (xx.xxx)	xx.x (xx.xxx)	xx.x (xx.xxx)	xx.x (xx.xxx)
		CV	XX.X	XX.X	XX.X	XX.X
		Median	XX.X	XX.X	XX.X	XX.X
		Min, Max	XX.X, XX.X	XX.X, XX.X	XX.X, XX.X	XX.X, XX.X
Repeat for Visits	4, 5 and 6.					
Test Product: Poo Reference: Condy Placebo: vehicle t	lofilox Topical G /lox® Gel 0.5% hat matches the t	tel 0.5%				
Source: <dataset< td="">>		Listing: 16.3.1		Snapshot Da	ata DD-MMM-YYYY	</dataset<>	>		Listing: 16.3.1		Snapshot Da	ata DD-MMM-YYYY
Program Name: <	Pgm name>		Date: YYYY-MM-DD 7	Time: HH:MM:SS	Programmer: <	<programmer initials=""></programmer>

Table 14.3.1.2Vital Signs Changes from Baseline, Safety Population

Protocol: 16-POD-001 Version 2.0, 15-Jan-2018

Confidential

Summary of Physical Examination, Safety Population						
Visit	Physical Examination	Statistic	Test Product	Reference	Placebo	All Subjects
Baseline (Day 0)	Height (cm)	n	XX	XX	XX	XX
		Mean (SD)	xx.x (xx.xxx)	xx.x (xx.xxx)	xx.x (xx.xxx)	xx.x (xx.xxx)
		CV	XX.X	XX.X	XX.X	XX.X
		Median	XX.X	XX.X	XX.X	XX.X
		Min, Max	XX.X, XX.X	XX.X, XX.X	XX.X, XX.X	XX.X, XX.X
	Weight (kg)	n	XX	XX	XX	XX
		Mean (SD)	xx.x (xx.xxx)	xx.x (xx.xxx)	xx.x (xx.xxx)	xx.x (xx.xxx)
		CV	XX.X	XX.X	XX.X	XX.X
		Median	XX.X	XX.X	XX.X	XX.X
		Min, Max	XX.X, XX.X	XX.X, XX.X	XX.X, XX.X	XX.X, XX.X
	General Appearance					
	Normal	n (%)	xx (xx.x)	xx (xx.x)	xx (xx.x)	xx (xx.x)
	Abnormal NCS	n (%)	xx (xx.x)	xx (xx.x)	xx (xx.x)	xx (xx.x)
	Abnormal CS	n (%)	xx (xx.x)	xx (xx.x)	xx (xx.x)	xx (xx.x)
	Not done	n (%)	xx (xx.x)	xx (xx.x)	xx (xx.x)	xx (xx.x)
	Heart Cardiovascular					
	Normal	n (%)	xx (xx.x)	xx (xx.x)	xx (xx.x)	xx (xx.x)
	Abnormal NCS	n (%)	xx (xx.x)	xx (xx.x)	xx (xx.x)	xx (xx.x)
	Abnormal CS	n (%)	xx (xx.x)	xx (xx.x)	xx (xx.x)	xx (xx.x)
	Not done	n (%)	xx (xx.x)	xx (xx.x)	xx (xx.x)	xx (xx.x)
	Lungs					
	Normal	n (%)	xx (xx.x)	xx (xx.x)	xx (xx.x)	xx (xx.x)
	Abnormal NCS	n (%)	xx (xx.x)	xx (xx.x)	xx (xx.x)	xx (xx.x)
	Abnormal CS	n (%)	xx (xx.x)	xx (xx.x)	xx (xx.x)	xx (xx.x)
	Not done	n (%)	xx (xx.x)	xx (xx.x)	xx (xx.x)	xx (xx.x)
	Gastrointestinal					
	Normal	n (%)	xx (xx.x)	xx (xx.x)	xx (xx.x)	xx (xx.x)
	Abnormal NCS	n (%)	xx (xx.x)	xx (xx.x)	xx (xx.x)	xx (xx.x)
	Abnormal CS	n (%)	xx (xx.x)	xx (xx.x)	xx (xx.x)	xx (xx.x)

Table 14.3.2Summary of Physical Examination, Safety Population

Confidential

Visit	Physical Examination	Statistic	Test Product	Reference	Placebo	All Subjects
	Not done	n (%)	xx (xx.x)	xx (xx.x)	xx (xx.x)	xx (xx.x)
	Ear/Nose/Throat					
	Normal	n (%)	xx (xx.x)	xx (xx.x)	xx (xx.x)	xx (xx.x)
	Abnormal NCS	n (%)	xx (xx.x)	xx (xx.x)	xx (xx.x)	xx (xx.x)
	Abnormal CS	n (%)	xx (xx.x)	xx (xx.x)	xx (xx.x)	xx (xx.x)
	Not done	n (%)	xx (xx.x)	xx (xx.x)	xx (xx.x)	xx (xx.x)
	Extremities					
	Normal	n (%)	xx (xx.x)	xx (xx.x)	xx (xx.x)	xx (xx.x)
	Abnormal NCS	n (%)	xx (xx.x)	xx (xx.x)	xx (xx.x)	xx (xx.x)
	Abnormal CS	n (%)	xx (xx.x)	xx (xx.x)	xx (xx.x)	xx (xx.x)
	Not done	n (%)	xx (xx.x)	xx (xx.x)	xx (xx.x)	xx (xx.x)
	Skin					
	Normal	n (%)	xx (xx.x)	xx (xx.x)	xx (xx.x)	xx (xx.x)
	Abnormal NCS	n (%)	xx (xx.x)	xx (xx.x)	xx (xx.x)	xx (xx.x)
	Abnormal CS	n (%)	xx (xx.x)	xx (xx.x)	xx (xx.x)	xx (xx.x)
	Not done	n (%)	xx (xx.x)	xx (xx.x)	xx (xx.x)	xx (xx.x)
	Other					
Repeat for EOS	S, ET visit and the change fror	n				
Baseline.						
NCS: Non-Clinica CS: Clinically Sig Test Product: Pod Reference: Condy Placebo: vehicle t	ally Significant gnificant lofilox Topical Gel 0.5% /lox® Gel 0.5% that matches the test product					
Source: <dataset></dataset>	>	Listing: 16.3.2			Snapshot Data Dl	D-MMM-YYYY
Program Name: <	Pgm name>	Date: YYYY-MM	M-DD Time: HH:MM:	:SS	Programmer: <prog< td="">rammer Initials>	</prog<>	rammer Initials>

Protocol: 16-POD-001 Version 2.0, 15-Jan-2018

Confidential

Week	Statistic	Test Product	Reference	Placebo	All Subjects
Week 1	n	XX	XX	XX	XX
	Mean (SD)	xx.x (xx.xxx)	xx.x (xx.xxx)	xx.x (xx.xxx)	xx.x (xx.xxx)
	CV	XX.X	XX.X	XX.X	XX.X
	Median	XX.X	XX.X	XX.X	XX.X
	Min, Max	XX.X, XX.X	XX.X, XX.X	XX.X, XX.X	XX.X, XX.X
Repeat for all Weeks	5				
Weekly Average	n	XX	XX	XX	XX
	Mean (SD)	xx.x (xx.xxx)	xx.x (xx.xxx)	xx.x (xx.xxx)	xx.x (xx.xxx)
	CV	XX.X	XX.X	XX.X	XX.X
	Median	XX.X	XX.X	XX.X	XX.X
	Min, Max	xx.x, xx.x	XX.X, XX.X	xx.x, xx.x	XX.X, XX.X

Mean, SD, Median, Min, and Max in Grams. Test Product: Podofilox Topical Gel 0.5% Reference: Condylox® Gel 0.5% Placebo: vehicle that matches the test product

Source: <Dataset>

Program Name: <Pgm name>

Listing: 16.3.3

Date: YYYY-MM-DD Time: HH:MM:SS

Snapshot Data DD-MMM-YYYY

Programmer: < Programmer Initials>

Protocol: 16-POD-001 Version 2.0, 15-Jan-2018

Confidential

	Summary of Study	Table 1 Drug Exposure, Number	4.3.4.1 of Applications by We	eek, Safety Population	
Week	Statistic	Test Product	Reference	Placebo	All Subjects
Week 1	n	XX	XX	XX	XX
	Mean (SD)	xx.x (xx.xxx)	xx.x (xx.xxx)	xx.x (xx.xxx)	xx.x (xx.xxx)
	CV	XX.X	XX.X	XX.X	XX.X
	Median	XX.X	XX.X	XX.X	XX.X
	Q1, Q3	XX.X, XX.X	XX.X, XX.X	XX.X, XX.X	XX.X, XX.X
Repeat for all Weeks					
Weekly Average	n	XX	XX	XX	XX
	Mean (SD)	xx.x (xx.xxx)	xx.x (xx.xxx)	xx.x (xx.xxx)	xx.x (xx.xxx)
	CV	XX.X	XX.X	XX.X	XX.X
	Median	XX.X	XX.X	XX.X	XX.X
	Q1, Q3	XX.X, XX.X	XX.X, XX.X	XX.X, XX.X	XX.X, XX.X

n: Number of Subjects

Mean, SD, Median, Min, and Max of number of applications during a week.

Test Product: Podofilox Topical Gel 0.5%

Reference: Condylox® Gel 0.5%

Placebo: vehicle that matches the test product

Source: <Dataset>

Listing: 16.3.4

Program Name: <Pgm name>

Date: YYYY-MM-DD Time: HH:MM:SS

Protocol: 16-POD-001 Version 2.0, 15-Jan-2018

Confidential

Week	Statistic	Test Product	Reference	Placebo	All Subjects
Week 1	n	XX	XX	XX	XX
	Mean (SD)	xx.x (xx.xxx)	xx.x (xx.xxx)	xx.x (xx.xxx)	xx.x (xx.xxx)
	CV	XX.X	XX.X	XX.X	XX.X
	Median	XX.X	XX.X	XX.X	XX.X
	Min, Max	XX.X, XX.X	XX.X, XX.X	XX.X, XX.X	XX.X, XX.X
Repeat for all Weeks					
Weekly Average	n	XX	XX	XX	XX
	Mean (SD)	xx.x (xx.xxx)	xx.x (xx.xxx)	xx.x (xx.xxx)	xx.x (xx.xxx)
	CV	XX.X	XX.X	XX.X	XX.X
	Median	XX.X	XX.X	XX.X	XX.X
	Min, Max	XX.X, XX.X	XX.X, XX.X	XX.X, XX.X	XX.X, XX.X

Table 14242

n: Number of Subjects

Mean, SD, Median, Min, and Max of hours from first application of the week to last application of the week.

Test Product: Podofilox Topical Gel 0.5%

Reference: Condylox® Gel 0.5%

Placebo: vehicle that matches the test product

Source: <Dataset> Listing: 16.3.4 Snapshot Data DD-MMM-YYYY Program Name: <Pgm name> Date: YYYY-MM-DD Time: HH:MM:SS Programmer: < Programmer Initials>

Protocol: 16-POD-001 Version 2.0, 15-Jan-2018

Confidential

	Summa	ary of Treatment Compl	iance (%) by Week, S	afety Population	
Week	Statistic	Test Product n (%)	Reference n (%)	Placebo n (%)	All Subjects n (%)
Week 1	n	XX	XX	XX	XX
	Mean (SD)	xx.x (xx.xxx)	xx.x (xx.xxx)	xx.x (xx.xxx)	xx.x (xx.xxx)
	CV	XX.X	XX.X	XX.X	XX.X
	Median	XX.X	XX.X	XX.X	XX.X
	Min, Max	XX.X, XX.X	XX.X, XX.X	XX.X, XX.X	XX.X, XX.X
Repeat for all Weeks					
Weekly Average	n	XX	XX	XX	XX
	Mean (SD)	xx.x (xx.xxx)	xx.x (xx.xxx)	xx.x (xx.xxx)	xx.x (xx.xxx)
	CV	XX.X	XX.X	XX.X	XX.X
	Median	XX.X	XX.X	XX.X	XX.X
	Min, Max	XX.X, XX.X	XX.X, XX.X	XX.X, XX.X	XX.X, XX.X

Table 14.3.5

n: Number of Subjects

Mean, SD, Median, Min, and Max of percentage of treatment compliance by week.

Test Product: Podofilox Topical Gel 0.5%

Reference: Condylox® Gel 0.5%

Placebo: vehicle that matches the test product

Source: <Dataset>

Listing: 16.3.5

Program Name: <Pgm name>

Date: YYYY-MM-DD Time: HH:MM:SS

Snapshot Data DD-MMM-YYYY

Programmer: < Programmer Initials>

Protocol: 16-POD-001 Version 2.0, 15-Jan-2018

Confidential

Table 14.3.6
Summary of Concomitant Medications by Preferred Term, Safety Population

WHO-DD ATC Class Level 1				
WHO-DD ATC Class Level 2	Test Product	Reference	Placebo	All Subjects
WHO-DD Preferred Term	n (%)	n (%)	n (%)	n (%)
Number of subjects with at least one concomitant				
medication	xx (xx.x)	xx (xx.x)	xx (xx.x)	xx (xx.x)
WIIO DD ATC Class Level 1	···· (··· ·· ··)			
WHO-DD ATC Class Level 1	XX (XX.X)	XX (XX.X)	XX (XX.X)	XX (XX.X)
WHO-DD ATC Class Level 2	xx (xx.x)	xx (xx.x)	xx (xx.x)	xx (xx.x)
WHO-DD Preferred Term 1	xx (xx.x)	xx (xx.x)	xx (xx.x)	xx (xx.x)
WHO-DD Preferred Term 2	xx (xx.x)	xx (xx.x)	xx (xx.x)	xx (xx.x)
etc.				
WHO-DD ATC Class Level 1	xx (xx.x)	xx (xx.x)	xx (xx.x)	xx (xx.x)
WHO-DD ATC Class Level 2	xx (xx.x)	xx (xx.x)	xx (xx.x)	xx (xx.x)
WHO-DD Preferred Term 1	xx (xx.x)	xx (xx.x)	xx (xx.x)	xx (xx.x)
WHO-DD Preferred Term 2	xx (xx.x)	xx (xx.x)	xx (xx.x)	xx (xx.x)
etc.				

Concomitant medications are coded using the World Health Organization Drug Dictionary (WHO-DD).

Test Product: Podofilox Topical Gel 0.5%

Reference: Condylox® Gel 0.5%

Placebo: vehicle that matches the test product

Source: <Dataset>

Listing: 16.3.6

Program Name: <Pgm name>

Date: YYYY-MM-DD Time: HH:MM:SS

Snapshot Data DD-MMM-YYYY

Programmer: < Programmer Initials>

Protocol: 16-POD-001 Version 2.0, 15-Jan-2018

Confidential

Site Reaction	Visit	Score	Test Product n (%)	Reference n (%)	Placebo n (%)	All Subjects n (%)
Ervthema	Baseline (Day 0)	Absent	xx (xx.x)	xx (xx.x)	xx (xx.x)	xx (xx.x)
		Present	$\mathbf{x}\mathbf{x}$ ($\mathbf{x}\mathbf{x}$. \mathbf{x})			
		Mild	xx (xx.x)	xx (xx.x)	xx (xx.x)	xx (xx.x)
		Moderate	xx (xx.x)	xx (xx.x)	xx (xx.x)	xx (xx.x)
		Severe	xx (xx.x)	xx (xx.x)	xx (xx.x)	xx (xx.x)
	Visit 3(Day7)	Absent	xx (xx.x)	xx (xx.x)	xx (xx.x)	xx (xx.x)
	· · /	Present	xx (xx.x)	xx (xx.x)	xx (xx.x)	xx (xx.x)
		Mild	xx (xx.x)	xx (xx.x)	xx (xx.x)	xx (xx.x)
		Moderate	xx (xx.x)	xx (xx.x)	xx (xx.x)	xx (xx.x)
		Severe	xx (xx.x)	xx (xx.x)	xx (xx.x)	xx (xx.x)
	Visit 3 Change					
	from Baseline	Absent	xx (xx.x)	xx (xx.x)	xx (xx.x)	xx (xx.x)
		Present	xx (xx.x)	xx (xx.x)	xx (xx.x)	xx (xx.x)
		Mild	xx (xx.x)	xx (xx.x)	xx (xx.x)	xx (xx.x)
		Moderate	xx (xx.x)	xx (xx.x)	xx (xx.x)	xx (xx.x)
		Severe	xx (xx.x)	xx (xx.x)	xx (xx.x)	xx (xx.x)

Table 14.3.7Summary of Site Reaction by Intensity and Visit, Safety Population

Repeat for Site reactions: dryness, burning/stinging, erosion, edema, pain, itching, and bleeding.

Then Repeat for visit 4, 5, 6 and EOS.

n: number of patients affected. Test Product: Podofilox Topical Gel 0.5% Reference: Condylox® Gel 0.5% Placebo: vehicle that matches the test product

Source: <Dataset>

Program Name: <Pgm name>

Listing: 16.3.7 Date: YYYY-MM-DD Time: HH:MM:SS

Protocol: 16-POD-001 Version 2.0, 15-Jan-2018

Confidential

	Overall Summary o	of Adverse Events, Safe	ety Population	
	Test Product (N=xxx) n (%)	Reference (N=xxx) n (%)	Placebo (N=xxx) n (%)	All Subjects (N=xxx) n (%)
Total number of AEs	XX	XX	XX	XX
Total number of SAEs	XX	XX	XX	XX
Total Number of TEAEs	XX	XX	XX	XX
Total Number of TESAEs	XX	XX	XX	XX
Number of Subjects with:				
At Least One TEAE	xx (xx.x)	xx (xx.x)	xx (xx.x)	xx (xx.x)
At Least One Related TEAE	xx (xx.x)	xx (xx.x)	xx (xx.x)	xx (xx.x)
At Least One Severe TEAE	xx (xx.x)	xx (xx.x)	xx (xx.x)	xx (xx.x)
At Least One TEAE Leading to				
Discontinuation	xx (xx.x)	xx (xx.x)	xx (xx.x)	xx (xx.x)
At Least One TEAE Leading to			× ,	
Death	xx (xx.x)	xx (xx.x)	xx (xx.x)	xx (xx.x)
At Least One TESAE	xx (xx.x)	xx (xx.x)	xx (xx.x)	xx (xx.x)
At Least One Related TESAE	xx (xx.x)	xx (xx.x)	xx (xx.x)	xx (xx.x)
At Least One Severe TESAE	xx (xx.x)	xx (xx.x)	xx (xx.x)	xx (xx.x)
At Least One TESAE Leading to		. ,		
Discontinuation	xx (xx.x)	xx (xx.x)	xx (xx.x)	xx (xx.x)

Table 14 3 8

(S)AE: (Serious) Adverse Event reported from signature of the Informed Consent Form to 30 days following the last study drug application. TE(S)AE: Treatment Emerging (Serious) Adverse Event reported during the treatment period (from the day of the first application of the study drug and up to the last visit). Test Product: Podofilox Topical Gel 0.5% Reference: Condylox® Gel 0.5% Placebo: vehicle that matches the test product

Source: <dataset></dataset>	Listings: 16.3.8.1 – 16.3.8.2 – 16.3.8.3	Snapshot Data DD-MMM-YYYY
Program Name: <pgm name=""></pgm>	Date: YYYY-MM-DD Time: HH:MM:SS	Programmer: < Programmer Initials>

Protocol: 16-POD-001 Version 2.0, 15-Jan-2018

Confidential

Table 14.3.8.1.1

Summary of Treatment Emergent Adverse Events (TEAEs) by System Organ Class and Preferred Term, Safety Population

	Test Product (N=xxx) n (%)	Reference (N=xxx) n (%)	Placebo (N=xxx) n (%)	All Subjects (N=xxx) n (%)
Total Number of AEs	XX	XX	XX	XX
Number of Subjects with at Least One AE	xx (xx.x)	xx (xx.x)	xx (xx.x)	xx (xx.x)
Number of subjects with at least One AE:				
System Organ Class #1	xx (xx.x)	xx (xx.x)	xx (xx.x)	xx (xx.x)
Preferred Term #1	xx (xx.x)	xx (xx.x)	xx (xx.x)	xx (xx.x)
Preferred Term #2	xx (xx.x)	xx (xx.x)	xx (xx.x)	xx (xx.x)
Preferred Term #3	xx (xx.x)	xx (xx.x)	xx (xx.x)	xx (xx.x)
etc.				
System Organ Class #2	xx (xx.x)	xx (xx.x)	xx (xx.x)	xx (xx.x)
Preferred Term #1	xx (xx.x)	xx (xx.x)	xx (xx.x)	xx (xx.x)
Preferred Term #2	xx (xx.x)	xx (xx.x)	xx (xx.x)	xx (xx.x)
Preferred Term #3	xx (xx.x)	xx (xx.x)	xx (xx.x)	xx (xx.x)
etc				

AE: Adverse Event reported from signature of the informed Consent Form to 30 days following the last study drug application.

N (%): Number of subjects and % of subjects, except for first line where it is specified as Number of AEs.

Test Product: Podofilox Topical Gel 0.5%

Reference: Condylox® Gel 0.5%

Placebo: vehicle that matches the test product

Source: <Dataset>

Listing:16.3.8.1

Program Name: <Pgm name>

Date: YYYY-MM-DD Time: HH:MM:SS

Snapshot Data DD-MMM-YYYY

Programmer: < Programmer Initials>

Protocol: 16-POD-001 Version 2.0, 15-Jan-2018

STATISTICAL ANALYSIS PLAN

Confidential

Table 14.3.8.1.2

Summary of Tretment Emergent Adverse Events (TEAEs) by System Organ Class, Preferred Term, and Severity, Safety Population

		Test Product	Reference	Placebo	All Subjects
		(N=xxx)	(N=xxx)	(N=xxx)	(N=xxx)
	Severity	n (%)	n (%)	n (%)	n (%)
Number of Subjects with at Least One TEAE	Mild	xx (xx.x)	xx (xx.x)	xx (xx.x)	xx (xx.x)
	Moderate	xx (xx.x)	xx (xx.x)	xx (xx.x)	xx (xx.x)
	Severe	xx (xx.x)	xx (xx.x)	xx (xx.x)	xx (xx.x)
	Total	xx (xx.x)	xx (xx.x)	xx (xx.x)	xx (xx.x)
Number of Subjects with at Least One TEAE:					
System Organ Class #1	Mild	xx (xx.x)	xx (xx.x)	xx (xx.x)	xx (xx.x)
	Moderate	xx (xx.x)	xx (xx.x)	xx (xx.x)	xx (xx.x)
	Severe	xx (xx.x)	xx (xx.x)	xx (xx.x)	xx (xx.x)
	Total	xx (xx.x)	xx (xx.x)	xx (xx.x)	xx (xx.x)
Preferred Term #1	Mild	xx (xx.x)	xx (xx.x)	xx (xx.x)	xx (xx.x)
	Moderate	xx (xx.x)	xx (xx.x)	xx (xx.x)	xx (xx.x)
	Severe	xx (xx.x)	xx (xx.x)	xx (xx.x)	xx (xx.x)
	Total	xx (xx.x)	xx (xx.x)	xx (xx.x)	xx (xx.x)

etc. TEAE: Treatment Emergent Adverse Event reported during the treatment period (from the day of the first application of the study drug and up to the last visit).

n (%): Number of subjects and % of subjects, except for first line where it is specified as Number of TEAEs.

Test Product: Podofilox Topical Gel 0.5%

Reference: Condylox® Gel 0.5%

Placebo: vehicle that matches the test product

Source: <Dataset>

Listing: 16.3.8.1

Program Name: <Pgm name>

Date: YYYY-MM-DD Time: HH:MM:SS

Protocol: 16-POD-001 Version 2.0, 15-Jan-2018

Confidential

Table 14.3.8.1.3

Summary of Treatment Emergent Adverse Events (TEAEs) by System Organ Class, Preferred Term, and Causality, Safety Population

		Test Product	Reference	Placebo	All Subjects
		(N=xxx)	(N=xxx)	(N=xxx)	(N=xxx)
	Causality	n (%)	n (%)	n (%)	n (%)
Number of Subjects	-				
with at Least One					
TEAE	Related	xx (xx.x)	xx (xx.x)	xx (xx.x)	xx (xx.x)
	Probably Related	xx (xx.x)	xx (xx.x)	xx (xx.x)	xx (xx.x)
	Possibly Related	xx (xx.x)	xx (xx.x)	xx (xx.x)	xx (xx.x)
	Probably not Related	xx (xx.x)	xx (xx.x)	xx (xx.x)	xx (xx.x)
	Not Related	xx (xx.x)	xx (xx.x)	xx (xx.x)	xx (xx.x)
	Total	xx (xx.x)	xx (xx.x)	xx (xx.x)	xx (xx.x)
Number of Subjects					
with at Least One					
TEAE:					
System Organ Class					
#1	Related	xx (xx.x)	xx (xx.x)	xx (xx.x)	xx (xx.x)
	Probably Related	xx (xx.x)	xx (xx.x)	xx (xx.x)	xx (xx.x)
	Possibly Related	xx (xx.x)	xx (xx.x)	xx (xx.x)	xx (xx.x)
	Probably not Related	xx (xx.x)	xx (xx.x)	xx (xx.x)	xx (xx.x)
	Not Related	xx (xx.x)	xx (xx.x)	xx (xx.x)	xx (xx.x)
	Total	xx (xx.x)	xx (xx.x)	xx (xx.x)	xx (xx.x)
Preferred Term					
#1	Related	xx (xx.x)	xx (xx.x)	xx (xx.x)	xx (xx.x)
	Probably Related	xx (xx.x)	xx (xx.x)	xx (xx.x)	xx (xx.x)
	Possibly Related	xx (xx.x)	xx (xx.x)	xx (xx.x)	xx (xx.x)
	Probably not Related	xx (xx.x)	xx (xx.x)	xx (xx.x)	xx (xx.x)
	Not Related	xx (xx.x)	xx (xx.x)	xx (xx.x)	xx (xx.x)

Protocol: 16-POD-001 Version 2.0, 15-Jan-2018

Confidential

TEAE: Treatment Emergent Adverse Event reported during the treatment period (from the day of the first application of the study drug and up to
the last visit)
n (%): Number of subjects and % of subjects, except for first line where it is specified as Number of TEAEs.
Test Product: Podofilox Topical Gel 0.5%
Reference: Condylox® Gel 0.5%
Placebo: vehicle that matches the test product

Source: <dataset></dataset>	Listings:16.3.8.1 - 16.3.8.3		Snapshot D	ata DD-MMM-YYYY
Program Name: <pgm name=""></pgm>	Date: YYYY-MM-DD Time: HH:MM:SS		Programmer: <programmer initials=""></programmer>	
Total	xx (xx.x)	xx (xx.x)	xx (xx.x)	xx (xx.x)
etc.				

Protocol: 16-POD-001 Version 2.0, 15-Jan-2018

STATISTICAL ANALYSIS PLAN

Confidential

Table 14.3.8.2

Summary of Treatment Emergent Serious Adverse Events (TESAEs) by System Organ Class and Preferred Term, Safety Population

	Test Product	Reference	Placebo	All Subjects
	(N=xxx)	(N=xxx)	(N=xxx)	(N=xxx)
	n (%)	n (%)	n (%)	n (%)
Total Number of TESAEs	XX	XX	XX	XX
Number of Subjects with at Least One TESAE	xx (xx.x)	xx (xx.x)	xx (xx.x)	xx (xx.x)
Number of subjects with at least One TESAE:				
System Organ Class #1	xx (xx.x)	xx (xx.x)	xx (xx.x)	xx (xx.x)
Preferred Term #1	xx (xx.x)	xx (xx.x)	xx (xx.x)	xx (xx.x)
Preferred Term #2	xx (xx.x)	xx (xx.x)	xx (xx.x)	xx (xx.x)
Preferred Term #3	xx (xx.x)	xx (xx.x)	xx (xx.x)	xx (xx.x)
etc.				
System Organ Class #2	xx (xx.x)	xx (xx.x)	xx (xx.x)	xx (xx.x)
Preferred Term #1	xx (xx.x)	xx (xx.x)	xx (xx.x)	xx (xx.x)
Preferred Term #2	xx (xx.x)	xx (xx.x)	xx (xx.x)	xx (xx.x)
Preferred Term #3	xx (xx.x)	xx (xx.x)	xx (xx.x)	xx (xx.x)
etc.				

TE(S)AE: Treatment Emergent (Serious) Adverse Event reported during the treatment period (from the day of the first application of the study drug and up to the last visit).N (%): Number of subjects and % of subjects, except for first line where it is specified as Number of TESAEs.

Test Product: Podofilox Topical Gel 0.5% Reference: Condylox® Gel 0.5% Placebo: vehicle that matches the test product

Source: <Dataset>

Listing: 16.3.8.2

Program Name: <Pgm name>

Date: YYYY-MM-DD Time: HH:MM:SS

Protocol: 16-POD-001 Version 2.0, 15-Jan-2018

Confidential

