1.2.3 Safety Profile

In clinical trials with Condylox® Gel 0.5%, the following local adverse reactions were reported during the treatment of anogenital warts:

Table 2. Local adverse reactions reported in Condylox® Gel 0.5% clinical trials

Adverse Reaction	Mild	Moderate	Severe
Inflammation	32.2%	30.4%	9.3%
Burning	37.1%	25.9%	11.5%
Erosion	27.0%	20.8%	8.9%
Pain	23.7%	20.4%	11.5%
Itching	32.2%	16.0%	7.8%
Bleeding	19.2%	3.0%	0.7%

The severity of local adverse reactions was predominantly mild or moderate and did not increase during the treatment period. Severe reactions were most frequent within the first 2 weeks of treatment.

Other local adverse reactions reported included stinging (7%), and erythema (5%); less commonly reported local adverse events included desquamation, scabbing, discoloration, tenderness, dryness, crusting, fissures, soreness, ulceration, swelling/edema, tingling, rash, and blisters. The most common systemic adverse event reported during the clinical studies was headache (7%).¹⁴

Further details are provided in the Investigator's Brochure [IB]¹⁵.

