- 6. Report any signs of adverse reactions to your study doctor. If the area you are putting study medication on is bleeding or swollen, or if there is excessive pain, burning or itching, stop applying it and contact your doctor.
- 7. Do not have sexual contact of any kind during the treatment period.
- 8. The study drug is flammable and must be kept away from open flames.

The subject will return used tubes of the study drug at the next visit along with completed Subject Diary Card. The Investigator will measure the weight of returned study medication using electronic scales. Measured weight of the study medication will be documented in a Study Drug Accountability Log.

If an additional treatment cycle is required, the Investigator will dispense the returned tube. If the remaining amount of the study drug in the used tube is not sufficient for another treatment cycle, study site will dispense a new tube of the study drug using the IRT system. The Investigator will measure the weight of study medication using electronic scales prior to providing to subject.

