6.3.5 Unscheduled Visit

Subjects will be encouraged to report any complications or adverse effects during their participation. Investigator may evaluate the subject at an unscheduled visit, if subject's condition will be considered as worsening. If the investigator assesses the subject's condition and determines that the subject's condition has worsened to the degree that it is unsafe for the subject to continue in the study, the subject may be discontinued from the study as a treatment failure, an Early Termination Visit conducted, and a standard of care treatment may be advised at the investigator's discretion. The following procedures should be performed at the Unscheduled Visit if required.

- Subject Diary Card Return, Review and Dispensation
- Adverse Events assessment

Confidential Page 39 of 59

- Concomitant and Prohibited Therapies review
- Collection of Vital Signs
- Physical examination
- Assessment of Local Application Site Reactions
- Visual Inspection of EAWs

Confidential Page 40 of 59

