7.6.3 Visit Windows

Visit windows for study 016-POD-001 are as follows:

Study Phase	Visit	Visit Name	Day
Screening	Visit 1	Screening	-14 to -1 days
Baseline	Visit 2	Baseline	Day 0
Follow-up	Visit 3	1 st Follow-up Visit (FU 1)	Day 7 (±1)
	Visit 4	2 nd Follow-up Visit (FU 2)	Day 14 (±1)
	Visit 5	3 rd Follow-up Visit (FU 2)	Day 21 (±1)
	Visit 6	End of Study	Day 28 (±5)
End of Study ¹	EOS	End of Study	Day1 – Day 28 (+5)
	ET	Early Termination Visit	From Screening to Day 28
	US	Unscheduled Visit	From Screening to Day 28 (+5)

1. If total disappearance of all warts is achieved within all treated areas at visits 2, 3, 4, or 5, respective visit will be considered an End of Study (EOS) visit.

Confidential

The flowchart for the study is as follows:

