7.6.4 Multiple Assessments

No multiple assessments for same visit are scheduled.

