Table 14.2.5.2.2	Number of Perianal Warts by Visit,	mITTs	Repeat
	Supplemental (including site 201)		
Table 14.2.6.1.1	Number of Genital and Perianal Warts by	PP	Unique
	Visit		
Table 14.2.6.1.2	Number of Genital and Perianal Warts by	PPs	Repeat
	Visit, Supplemental (including site 201)		
Table 14.2.6.2.1	Number of Genital and Perianal Warts by	mITT	Repeat
	Visit		
Table 14.2.6.2.2	Number of Genital and Perianal Warts by	mITTs	Repeat
	Visit, Supplemental (including site 201)		
Table 14.2.7.1.1	Warts Area (cm ²) by Visit	PP	Unique
Table 14.2.7.1.2	Warts Area (cm ²) by Visit, Supplemental	PPs	Repeat
	(including site 201)		
Table 14.2.7.2.1	Warts Area (cm ²) by Visit	mITT	Repeat
Table 14.2.7.2.2	Warts Area (cm ²) by Visit, Supplemental	mITTs	Repeat
	(including site 201)		
Safety			
Table 14.3.1.1	Summary of Vital Sign	Safety	Unique

Protocol: 16-POD-001 Version 2.0, 15-Jan-2018

Confidential

Display Number		Population	Unique/Repeat
Table 14.3.1.2	Vital Signs Changes from Baseline	Safety	Unique
Table 14.3.2	Summary of Physical Examination	Safety	Unique
Table 14.3.3	Summary of Study Drug Exposure, Dose in	Safety	Unique
	grams by Week		
Table 14.3.4.1	Summary of Study Drug Exposure, Number	Safety	Unique
	of Applications by Week		
Table 14.3.4.2	Summary of Study Drug Exposure, Duration	Safety	Unique
	of Exposure in Hours by Week		
Table 14.3.5	Summary of Treatment Compliance (%) by	Safety	Unique
	Week		
Table 14.3.6	Summary of Concomitant Medications by	Safety	Repeat
	Preferred Term		
Table 14.3.7	Summary of Site Reaction by Intensity and	Safety	Unique
	Visit		
Table 14.3.8	Overall Summary of Adverse Events	Safety	Unique
Table 14.3.8.1.1	Summary of Treatment Emergent Adverse	Safety	Unique
	Events (TEAEs) by System Organ Class and		
	Preferred Term		
Table 14.3.8.1.2	Summary of Treatment Emergent Adverse	Safety	Unique
	Events (TEAEs) by System Organ Class,		
	Preferred Term, and Severity		
Table 14.3.8.1.3	Summary of Treatment Emergent Adverse	Safety	Repeat
	Events (TEAEs) by System Organ Class,		
	Preferred Term, and Causality		
Table 14.3.8.2	Summary of Treatment Emergent Serious	Safety	Unique
	Adverse Events (TESAEs) by System Organ		
	Class and Preferred Term		

Confidential

Table 14.1.1.1.1 Subject Disposition, All Subjects

Population	Test Product n (%)	Reference n (%)	Placebo n (%)	All Subjects n (%)
All Subjects	xx (xx.x)	xx (xx.x)	xx (xx.x)	xx (xx.x)
Safety Population	xx (xx.x)	xx (xx.x)	xx (xx.x)	xx (xx.x)

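### Table 14.3.7, the only summary of the local reaction scores, has no row for Unscheduled visits, leaves the place of Early Termination scores unclear, and shows no worst score per subject

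*SAP*

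**What the plan says.** Protocol 2.2.2 makes the local application site reaction scores, over the period of study drug application, a secondary (safety) endpoint. Protocol 6.2.1.7 has eight reactions scored 0 to 3 at every study visit. The same assessment is on the procedure lists for the EOS/ET visit (Protocol 6.3.4) and, if required, the Unscheduled visit (Protocol 6.3.5).

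SAP 10.1.2 plans a summary by type of reaction and intensity score, with the number and percentage of subjects affected. It excludes no kind of visit. The SAP list of tables has one entry for these scores, Table 14.3.7, "Summary of Site Reaction by Intensity and" visit. Its shell sets out Baseline, Visit 3 and the Visit 3 change from baseline, and then instructs: "Then Repeat for visit 4, 5, 6 and EOS". Listing 16.3.7, the by-subject listing behind it, carries the labels Baseline, Visits 3 to 5, ET, EOS and US (Unscheduled).

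SAP 7.6.3 gives EOS, ET ("Early Termination Visit") and US separate rows with separate windows. SAP 7.6.4 says only this: "No multiple assessments for same visit are scheduled". SAP 7.6.5 allows no imputation for the Safety population.

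**The concern.** Local tolerability compared with the reference and the vehicle is the secondary objective. The protocol gives subjects a route to the clinic between scheduled visits. Protocol 6.3.5 states: "Subjects will be encouraged to report any complications or adverse effects during their participation". Protocol 5.7.1 tells a subject with bleeding, swelling or excessive pain, burning or itching to "stop applying it and contact your doctor". An Unscheduled visit is therefore a plausible place for a score to be taken close to a reaction, and it is the one kind of visit with no place in the summary table.

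The shell is also built visit by visit. The endpoint refers to the whole application period, but no row says how many subjects in each arm ever had a moderate or severe score. The visit rows cannot be combined to give that number, because the same subject may appear in several of them. At stake is how completely the descriptive safety section reports local reactions.

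**Working it through.** The plan states no figure to reproduce. The check is a comparison of texts plus one piece of date arithmetic.

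**1. Where a score is taken and where it is shown**

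| Visit | Score collected (Protocol) | Label in Listing 16.3.7 | Row in Table 14.3.7 |
|---|---|---|---|
| Baseline | Yes (6.3.2) | Yes | Yes |
| Visits 3–5 | Yes (6.3.3) | Yes | Yes |
| Visit 6 | Yes (6.3.3) | No label of its own | Yes |
| EOS | Yes (6.3.4) | Yes | Yes |
| ET | Yes (6.3.4) | Yes | Not named |
| Unscheduled | If required (6.3.5) | Yes | Not named |

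**2. Unscheduled visits.** No rule in the SAP assigns an Unscheduled score to a scheduled visit. SAP 7.6.3 treats it as a separate visit, SAP 7.6.4 gives no mapping, and nothing is carried forward in the Safety population (SAP 7.6.5). On any reading these scores are listed but not summarised.

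**3. Early Termination.** The SAP points both ways.
- *ET under Visit 6/EOS.* SAP 3.1 describes Visit 6 as the End of Study or Early Termination visit. The schedule in SAP 3.2 heads that column EOS/ET, as does Protocol Appendix B, and Protocol 6.3.4 has one procedure list for both. Listing 16.3.7 has seven visit labels but cites six sets of CRF pages (32–34, 49–51, 63–65, 75–77, 89–91, 122–124), and none of the labels is Visit 6. The natural inference is that EOS and ET share a form and that the Visit 6 row draws on it.
- *ET separate.* SAP 7.6.3 gives ET its own row and window, Table 14.3.2 repeats for EOS and for ET, and Listing 16.3.7 keeps the labels apart.

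The first reading is the more likely one, but no sentence says so. Under it, a subject who stops in the second week, and is seen as soon as possible as Protocol 6.3.4 requires, could have that score reported in a row labelled Day 28.

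**4. Timing of the scheduled rows.** Protocol 3.1 gives the application days and the visit days. Days from the last application of each cycle to the visit:
- Cycle 1: 7 − 3 = 4
- Cycle 2: 14 − 10 = 4
- Cycle 3: 21 − 17 = 4
- Cycle 4: 28 − 24 = 4

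With the ±1 day window at Visits 3 to 5, the range is 3 to 5 days if applications are on the nominal days. Protocol 6.2.1.7 gives no look-back period for the score, so I read it as the state of the skin at the visit. On that reading, a reaction that peaks during the three application days and settles in the rest period is scored after its peak.

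**5. Size.** The documents give no expected number of ET or Unscheduled visits and no distribution of scores at them. The number of affected scores, and any difference between arms, cannot be computed.

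**The case against.** The strongest reply is that the reactions are summarised elsewhere. Protocol 6.2.1.7 requires every application site reaction to be recorded as an adverse event. SAP 10.1.1 counts a subject at the greatest severity within a preferred term, and Table 14.3.8.1.2 tabulates treatment-emergent events by term and severity. That is already a subject-level worst-severity summary, and it covers ET and Unscheduled visits. Table 14.3.8 adds events leading to discontinuation. The reply stands as partial cover. It does not close the gap, because adverse event severity is defined by tolerability and interference with usual activities (Protocol 7.2), while the endpoint is the 0–3 intensity score.

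It can also be said that scheduled visits catch most of what matters. Protocol 1.2.3 reports that "Severe reactions were most frequent within the first 2 weeks of treatment", and Visits 3 and 4, on Days 7 and 14, score that period. A subject who continues after an Unscheduled visit is scored again at the next scheduled one. Both points have weight, and both limit the likely effect.

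A reader might go further and infer that ET scores are left out of the endpoint. The documents do not support that. The endpoint and SAP 10.1.2 are not limited by visit, the scores are listed, and Visit 6 is labelled EOS/ET in several places. A reader might also infer that the worst reactions are seen at ET and Unscheduled visits. That is not documented: Protocol 4.2 lists many reasons for leaving the study, including withdrawn consent, non-compliance, treatment failure and loss to follow-up.

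**Conclusion.** This is a reporting gap in a descriptive safety table. It is definite for Unscheduled scores and a matter of unclear labelling for ET scores. Because the scheduled rows are snapshots nominally four days after the last application of each cycle, and no row counts each subject's worst score, Table 14.3.7 can understate the worst reaction per subject over the application period.

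This rests on two assumptions: that the score describes the state at the visit, and that some subjects have a higher score at an Unscheduled or ET visit than at any scheduled one. The first fits the wording of the protocol. The second is plausible, but its frequency is unknown.

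It may be tempting to conclude that the comparison between arms is biased toward similarity. That would need the share of severe scores seen only at unplanned visits, arm by arm, and the documents give nothing on it. Neither the size nor the direction can be stated. The equivalence and superiority analyses use treatment success only and are unaffected. The point is worth raising as a cheap improvement, not as a defect that threatens a conclusion.

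**What to change.** In Table 14.3.7, for each reaction and arm, add one subject-level block: *Worst post-baseline score at any visit (scheduled, EOS, ET or Unscheduled)*. Count each Safety-population subject with a post-baseline score once. State the denominator in the footnote, because SAP 7.4 otherwise bases percentages on all subjects in the treatment group.

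Add one sentence, in SAP 7.6.3 or 10.1.2, saying whether ET scores are shown under Visit 6/EOS or in a row of their own.

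The data are already in Listing 16.3.7, so nothing new is collected. SAP 7.4 lets layout changes to the shells pass without a revision. The ET rule concerns data handling and should be written into the text. The cost is a few more rows and some programming, and the reported reaction rates may look slightly less favourable.
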